Based on the results of the DNB, patients and their clinician selection the mutually selected most appropriate treatment streams: altered toxin dosage, surgical micro fascicular neurectomy, percutaneous cryoneurotomy, radiofrequency neurotomy, surgical tenotomy, or unlikely to benefit from further procedures. The choice of which stream is based on the response of the nerve block. All patients with contracture will need a tendon or muscle surgery to improve range of motion. Patients with increased range of motion in isolated regions, such as the shoulder adductors, elbow flexors, can undergo cryoneurotomy on their isolated motor nerve. Patients with increased range of motion in the finger and wrist flexors require nerve surgery as well as possible muscle and tendon surgery to the motor fibres cannot isolated for nerve ablation in the region. The decision to not offer a procedure and increase toxin is reserved for the milder cases where range of motion is quite good, but the nerve block reveals even more loosening. This group will not be part of our study as that is the typical course of treatment.

Beginning of Study:

After surgical or percutaneous neuroablative procedures are selected patients will be invited to enroll in the study.

There will be no change in usual care after the procedures. Units of BoNT used will be tracked. All patients will be assessed at each stage by a single assessor to administer measurements and test scores. This study is not blinded. Blinding is not typical in surgical studies. It is too difficult to hide scars. The skin will need to be exposed to ensure proper measurements. The assessor would also intuitively guess by the deformity of the arms which procedures were most likely undertaken.

Initial Contact Letter:

Once a patient elects to undergo a nerve or surgical procedure they will receive a study information package at the time of decision. All patients have routine follow ups in clinic and the assessment will be done in the same days of their visits. All patients will be offered to take the package home to consider or fill out in clinic. Patients will receive one reminder phone call or email at their preference to determine if they will participate. All patients will be given a reminder call by our research assistant two weeks after unless they opt out.

Surgical Neurectomy Stream.

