The protocol follows the same assessment and preparation as cryoneurotomy. [name] has performed thousands of these interventions to nerves. They are also percutaneous nerve procedures. The protocol is quite similar as cryoneurotomy, with the exception of the probe. Pulsed radiofrequency (PRF), a technique introduced in the 1990's³³, is known to be safe and effective on nerve structures and particularly relieving pain. It delivers an electrical field and heat bursts to targeted nerves or tissues without damaging these structures. Previous studies have used continuous radiofrequency (CRF)³⁴ exposes target nerves or tissues to a continuous electrical stimulation and ablates the structures by increasing the temperature around the RF needle-tip. PRF does not produce sufficient heat to cause structural damage. The availability of cryoneurotomy is quite limited to the lack of machines in Canada, where as radiofrequency is widely performed in hospitals and clinics all across Canada. To date our availability of time on the cryoneurotomy equipment is limited, and pulsed radiofrequency will allow for shorter waits.

Sample Size Justification. Statistical Analysis

Sample Size: N = 50

This is a pilot study. A convenience sample of 50 patients is anticipated, based on the volume of patients that has been triaged in this clinic to date. Over 100 patients have been triaged in 18 months, so it is anticipated that 50 target patients to be fully completed treatment in 18 months. At 4-6 (divided between surgical and interventional) patients per month for 12 months, this is achievable based on this clinical experience. Analysis will be individualized per patient, as each will undergo a unique procedure. Statistical analysis will address each patient stream individually. The outcome measures that will used are standard clinical and functional measures, but effect sizes are not readily available from previous studies in order to formally calculate sample size. Furthermore, this study uses an exploratory prospective cohort design, rather than a parallel group trial design, limiting the rationale for providing a sample size calculation.

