To confirm that improvements in outcomes are statistically significant a paired t-test on the difference of proportions, applicable to pre-treatment and post-treatment, will be performed. Pearson's correlation and logistic regression will also be used to determine whether any key predictors are associated with any of the outcomes at final visit. We will employ repeated measures or linear mixed (multilevel) models of change to analyze within-person trajectories in all key outcomes for the intensive repeated measures data spanning the 12-month study period. Such models derive individual parameter estimates for baseline function and change pursuant to nerve or surgical procedure, and will directly index the magnitude in improvement for each outcome (pursuant to treatment) with each individual serving as their own control (i.e., with change indexed relative to each individual's own personal baseline).

If normal distribution in the outcomes does not stand, McNemar's test and Spearman correlation will be calculated instead of paired t-test and Person's correlation, respectively.

We will rely on Island Health Statistic for this process, the data will not leave Island Health and will be analyzed through REDCap. (Statistics provided by [name], Island Health)

Inclusion Criteria:

- Adult patient \geq 18 years old, with upper extremity spasticity causing functional impairment.
- Patients that have plateaued in outcomes in which the clinical examination suggests further interventions can be trialled.
- The clinical examination, including a V1 (maximal passive stretch) and V3 (Fast catch) on upper extremity examination that demonstrates further passive or active range may be possible, versus if contracture must be managed. For example, a fistled hand that can be forced open. This includes factors such as fluctuating tone or clonus interfering with assessment.
- The patient undergoes a diagnostic nerve block to determine if there is a reducible spasticity in the muscle versus contracture.
- The patient has been offered a neuroablative procedure or surgery and has elected to undergo the procedure. The patient has consented to undergo said procedure.

Exclusion Criteria:

[figure not shown]
- Patients where no consent or Assent is obtained
- Unable attend treatment schedule

Efficacy Evaluation/Schedule/length of the study:

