Patients will be recruited over a one-year period. All patients would have already been screened and elected to undergo one of the procedures with consent to procedure. All patients will require baseline measurements prior to their procedure. Efficacy will be measured by their assessments after the procedure using our outcome measures, including a twelve months follow up for the initial study but will remain for up to 24 months.

Visual Timeline:

Clinical Care and Research Activity Timelines

*Note, you may have more than one type of procedure, based on your response/recovery. You and your doctor would discuss this as it is a clinical decision. (standard clinical care)

Time required to complete study (months):

24 months.

Access to Patient Charts:

As part of our usual standard of care. The charts will be accessed by the treating physicians. The research assistant will require chart access to plot demographics and contact patients.

Incidental Findings:

Incidental findings are not expected in the ablation procedures as this is percutaneous and the ultrasound of the limb would have been done on two previous occasions. While not expected in upper

extremity surgery, surgical incidental findings include, abnormal anatomy, tumours. Any incidental finding would be reviewed with the patients and investigated fully by the research team and or their primary care givers, with appropriate referrals and imaging found.

Stopping rules:

[figure not shown]
The study would be stopped by the clinical team in the advent of treatment failure, or adverse events in conjunction with the CEC. It would be stopped if the REB or Health Authority stops the trial over research concern. Loss of funding is an unlikely cause of stopping as the treatments are funded, it is only the data collection salary that provides the largest expenditure.

References:

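### Key predictors are tested against final-visit values without baseline, and the models of change state no predictor term, so no stated analysis relates a predictor to improvement

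*Combined protocol and SAP*

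**What the plan says.** In the combined protocol and SAP, the section on sample size and statistical analysis describes three steps.

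- **Before-after test.** A paired comparison of pre- and post-treatment values. This point does not touch it.
- **Predictor analysis.** Pearson's correlation and logistic regression are to show "whether any key predictors are associated with any of the outcomes at final visit". If outcomes are not normal, Spearman replaces Pearson. No baseline covariate or change score is mentioned, and the predictors are not named.
- **Mixed models.** Repeated-measures or linear mixed models follow each person over 12 months and "will directly index the magnitude in improvement for each outcome", with change measured from that person's own baseline. Their terms are not listed, and no predictor or predictor-by-time term is stated.

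The same section says "Statistical analysis will address each patient stream individually" and that "this study uses an exploratory prospective cohort design, rather than a parallel group trial design". Design Details names four procedure streams: "surgical micro fascicular neurectomy, percutaneous cryoneurotomy, radiofrequency neurotomy, surgical tenotomy". On data, the efficacy section says "All patients will require baseline measurements prior to their procedure". It describes follow-up as "including a twelve months follow up for the initial study but will remain for up to 24 months", so the final visit is not tied to one time point. The timeline note tells patients that "you may have more than one type of procedure, based on your response/recovery".

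The Hypothesis section is about improvement in range of motion, function and satisfaction.

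**The concern.** The one stated analysis that contains predictors leaves out baseline, and the one that uses baseline states no predictors. Patients in this population start from very different levels, as the Study Design section says. A patient characteristic that goes with a better starting arm may therefore correlate with a better final arm even if it says nothing about how much the arm gained. The reverse can also happen: a characteristic that goes with a worse start but a larger gain may show no correlation with the final value.

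The hypothesis is about improvement, and the background stresses patient selection. Readers are therefore likely to take a significant predictor as a sign of who improves, and the planned correlation cannot support that reading.

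Goal Attainment is exempt. Every patient starts at -1, so the final value and the gain differ only by a constant.

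**Working it through.** **Inputs.** From the documents: N = 50, four procedure streams, and baseline measured in everyone. The documents give no correlations, stream sizes or significance level. Assumed here: normal data, two-sided 5%, no dropout, stream sizes of 25 or 12 (50/4 = 12.5), and the correlations shown. The plan states no figure for this analysis that could be reproduced.

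Write a = correlation of predictor with baseline, and b = correlation of baseline with final value.

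**Step 1. The predictor adds nothing once baseline is known.** The correlation of predictor with final value is then a × b. At (0.5, 0.6) it is 0.30. By Fisher's z at n=50, atanh(0.30) × √47 = 0.3095 × 6.856 = 2.12, and P(Z > 1.96 − 2.12) ≈ 56%. Simulation (40,000 runs) gives the share of studies with p < 0.05:

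| a, b | Pearson, n=50 | n=25 | n=12 | with baseline as covariate |
|---|---|---|---|---|
| 0.5, 0.6 | 56.8% | 31.6% | 15.8% | about 5% |
| 0.3, 0.6 | 24.0% | 13.8% | 8.5% | about 5% |
| 0.5, 0.3 | 18.1% | 11.1% | 7.5% | about 5% |
| 0.3, 0.3 | 9.7% | 7.2% | 5.7% | about 5% |

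Spearman does not help. With a six-grade outcome at (0.5, 0.6) it gives about 51% at n=50 and 14% at n=12. A linear model on the grade with baseline gives 5–6% at both sizes.

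**Step 2. The reverse error.** With a real effect of 0.30 SD given baseline, a = −0.5 and b = 0.6, the correlation with the final value is 0.30 − 0.5 × 0.6 = 0. At n=50 the plain correlation finds it in 5% of runs and the adjusted model in 57%.

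**Step 3. The predictor is unrelated to change from baseline, with equal variances.** This is a different null. Predictor and final value now correlate at a, and the partial correlation given baseline is a(1 − b)/√[(1 − a²)(1 − b²)].

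- (0.5, 0.6): 0.5 × 0.4/√(0.75 × 0.64) = 0.289. At n=50, Pearson flags 97%, baseline adjustment 53%, the change score 5%.
- (0.5, 0.3): 0.5 × 0.7/√(0.75 × 0.91) = 0.424. At n=50, Pearson flags 97%, baseline adjustment 87%.

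The change score in turn flags about 34% under the null of Step 1 at (0.5, 0.6), n=50. Neither analysis can stand in for the other.

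**Step 4. What adjustment costs or gains.** Take a predictor unrelated to baseline that correlates 0.3 with the final value, at n=50. Adding baseline moves power from 57% to 77% if b = 0.6, from 57% to 60% if b = 0.3, and from 57.1% to 56.5% if b = 0.

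For a predictor tied to baseline, the ratio of confidence-interval half-widths (adjusted to unadjusted) is √{[(1 − b²)/((1 − a²) df₁)] / [(1 − a²b²)/df₀]} times the ratio of t critical values. At a = 0.7, with b from 0.7 to 0.3:

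- n=50, baseline plus three stream terms (df 48 to 44): 1.20 to 1.43.
- n=50, baseline only (df 48 to 47): 1.16 to 1.38.
- A stream of 12, baseline only (df 10 to 9): 1.23 to 1.46.

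**The case against.** **The correlation does what the text claims.** The section speaks only of association with final outcomes, and Pearson tests that validly. The analysis is exploratory, in a pilot, and is not a listed objective. This stands. A reader might infer that the planned correlation is a statistical error; the documents do not support that. The gap is that nothing stated reaches improvement.

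**The mixed models may contain predictors.** The section does not list their terms, so their absence is read from silence. This stands in part: the models could carry a predictor-by-time term, and that is one of the remedies below. As written, they are described only for trajectories and size of improvement.

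**Baseline adjustment does not identify predictors of gain either.** This stands if gain means change from personal baseline, which is how the section describes improvement. Step 3 shows 53% and 87% flagged. A reader might infer that adding baseline separates who improves from who merely started better. It does so only for association with the final value given baseline, and only with a reliable baseline. At reliability 0.8, with true gain unrelated to the predictor, adjustment leaves about 12% at n=50, against 78% unadjusted.

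**The 57% is not the planned analysis.** The plan works by stream. At about 12 per stream the excess is 6–16%, and every correlation is assumed. This stands.

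**Pooling would override the by-stream choice.** This stands. A pooled model assumes common slopes across streams that treat different problems. The gain is precision: an interval from one stream of 12 is about 2.5 times as wide as from the pooled 50.

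**Logistic regression can take baseline as a covariate.** True. The absence of a stated cut-off for any outcome is a separate missing detail and adds nothing to this point.

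**Conclusion.** The point holds as a minor, cheap improvement. No stated analysis can show whether a predictor relates to improvement.

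Under the stated assumptions, a predictor that adds nothing given baseline reaches significance in about 57% of studies at n=50 and 16% in a stream of 12 when the correlations are (0.5, 0.6). At (0.3, 0.3) this falls to 10% and 6%. With baseline as a covariate it is about 5% throughout, given a reliably measured baseline. The point does not apply to Goal Attainment, nor to a predictor that is itself the baseline value of the outcome.

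Two stronger conclusions are not supported. The before-after comparison is unaffected. And no version of the predictor analysis shows who benefits from a procedure, because there is no untreated group; the results are prognostic and exploratory.

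**What to change.** 1. **Keep the correlation**, labelled as a description of association with final status.
2. **Add a regression** for each outcome except Goal Attainment: the 12-month value on the predictor plus the baseline value of the same outcome. Report it as association with the 12-month value given baseline. Naming 12 months also settles which visit is final.
3. **If predictors of change itself are meant, say so**, and add a predictor-by-time term to the mixed model already planned. State in advance which of the two questions is intended, because the answers may differ.
4. **Follow the by-stream analysis.** Define stream by the first study procedure, since patients may have more than one type. A pooled model with stream terms is optional; if used, state that it is for this analysis only and assumes common slopes.
5. **Describe the results as exploratory and prognostic.**

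**Cost.** Wording only, since baseline is already collected. Each model loses one degree of freedom (48 to 47 at n=50, 10 to 9 in a stream of 12); the optional stream terms take three more. If baseline and final values are uncorrelated and the predictor is unrelated to baseline, the loss is about 1 point of power. If the predictor is strongly tied to baseline (0.7), intervals widen by 20–43% in the pooled model with stream terms, and by 23–46% in a stream of 12.

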5- Changes in hand function as assessed by House Functional Scale (1981)³⁵. The test will be done by an independent examiner and participants will be asked to pick a cube on the table while they are in a sitting position. Based on the available scale (0= No movement and 8= spontaneous use, complete) their hand function will be graded in baseline, 1,3,6,9 and 12 months after intervention.

6-Changes in hand grip strength as assessed by dynamometer and will be recorded in KG in baseline and 1,3,6,9 and 12 months. The test will be done by Jamar Dynamometer and will be recorded as KG.

Hypothesis:

Surgical or percutaneous ablative procedures can improve range of motion, function and patient satisfaction in patients that have plateaued or are refractory to botulinum focused therapies after screening patients with an ultrasound (US)-guided electrical (e)-stimulation DNB with 2% lidocaine to determine the most responsible muscle(s) in the spastic upper extremity.

Study Design:

This cohort study has a prospective intensive repeated measures study design. Repeated measures design is a research design that involves multiple measures of the same variable taken on the same subjects either under different conditions or over two or more time periods. Intensive denotes more measurements over time. Patients diagnosed with spasticity vary widely in function and limb usage; thus, the benefit of using this design is that it allows participants to serve as their own control.

Design Details:

Patients with upper extremity spasticity will be recruited from the multidisciplinary spasticity clinic. All study patients will have been assessed in the interdisciplinary team consisting of a physiatrist, hand surgeon, and an interventional anesthesiologist. US-guided e-stimulation DNB with 2% lidocaine will be used as a screening tool to determine the most responsible muscle(s) for the spastic upper extremity. Pre- and post-block maximum active and passive range of motion in the spastic muscle group., and the presence of fixed joint contractures will be assessed.

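### The paired t-test is dropped for McNemar's test when the outcomes look non-normal, but that test rests on within-patient differences, so a valid test can be discarded and most of its power lost

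*Combined protocol and SAP*

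**What the plan says.** All of this is in the combined protocol and SAP.

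- **Pre/post test** (Sample Size Justification. Statistical Analysis): "a paired t-test on the difference of proportions, applicable to pre-treatment and post-treatment, will be performed". No proportion or responder cut-off is defined anywhere.
- **Switch** (same section): "If normal distribution in the outcomes does not stand, McNemar's test and Spearman correlation will be calculated instead", and this is "instead of paired t-test and Person's correlation, respectively". The plan does not say how normality is judged, at which visit, or whether on measured values or changes.
- **Longitudinal analysis** (same section): "We will employ repeated measures or linear mixed (multilevel) models of change to analyze within-person trajectories in all key outcomes". No normality condition and no fallback is attached to it.
- **Unit of analysis** (same section): "Statistical analysis will address each patient stream individually". The total is 50, a convenience sample, and numbers per stream are not given.
- **Reason for the own-control design** (Study Design): "Patients diagnosed with spasticity vary widely in function and limb usage".
- **Outcomes** (Primary Objectives and Secondary Objective): ordinal grades (Ashworth, Keenan, House), degrees, DASH from 0 to 100, a goal attainment score, a pain score, a block count and grip in kg.

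**The concern.** A paired t-test needs the within-patient differences to be roughly normal, or the sample large enough for their mean to be. It places no condition on the baseline or follow-up values. The protocol adopts an own-control design because patients differ so much from one another. A normality check on the outcomes therefore mostly reads that between-patient spread, which the paired test has already removed.

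Two errors can follow. The check can fail when the differences are well behaved, and a valid test is discarded. Or it can pass when the differences are skewed, and a poorly calibrated test is kept.

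The first error is made costly by what replaces the t-test. McNemar's test is for paired binary data, so each score must first be cut in two, at a point the plan does not define. The stake is the test the plan uses to declare improvements significant.

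**Working it through.** **The plan's own figure.** There is none to reproduce: the section gives no effect size, SD, alpha or power. The distributions, the check and the cut-point below are therefore assumptions.

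**Why the check misses.** Write patient *i*'s baseline as *u_i* + *e_i0* and follow-up as *u_i* + δ_i + *e_i1*. The difference is δ_i + *e_i1* − *e_i0*, and *u_i* cancels. The paired statistic, t = mean(d) / (SD(d)/√n), never sees *u_i*. The shape of the outcomes is dominated by *u_i* when patients vary widely.

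**Sample sizes used.** n = 50 is the whole cohort. An equal split (assumed) over the four procedural streams in Design Details gives 50/4 = 12.5, so n = 12. A split into surgical and percutaneous gives 50/2 = 25.

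**Check used.** Shapiro-Wilk at 5% on baseline or follow-up values; tests two-sided at 0.05; 4,000 simulated samples per setting.

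**1. Valid t-test discarded.** Scores are bimodal around 35 and 80 (SD 8). Change is normal with SD 12 and mean half an SD (6 points). McNemar is cut at the baseline median.

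| n | t-test dropped | Power, paired t | Power, plan's rule | Power, same trigger with Wilcoxon |
|---|---|---|---|---|
| 12 | 61% | 0.36 | 0.14 | 0.34 |
| 25 | 97% | 0.66 | 0.09 | 0.64 |
| 50 | 100% | 0.93 | 0.30 | 0.92 |

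Loss under the plan's rule: 0.36 − 0.14 = 0.22, 0.66 − 0.09 = 0.57, 0.93 − 0.30 = 0.63. Loss with a Wilcoxon fallback: 0.02, 0.02 and 0.01. As a rough check at n = 12, the t-test survives in 39% of samples and 0.39 × 0.36 = 0.14, so almost all the remaining power comes from samples where the switch did not fire. A check on the differences would have flagged only about 5%.

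A second set of assumptions (modes 30 and 80, difference SD 10, n = 10/25/50) agrees. The t-test is dropped in 74% of samples at n = 10 and in over 99% at 25 and 50, although its type I error is correct (0.045 to 0.053). Power is 0.07/0.04/0.11 under the rule, against 0.30/0.66/0.94 for the t-test and 0.29/0.64/0.93 for Wilcoxon.

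**2. Poorly calibrated t-test kept.** Scores are normal and differences are exponential with mean zero. The outcome check keeps the t-test in about 91% of samples. Its type I error when kept is 0.105/0.083/0.063 at n = 10/25/50. A check on the differences would flag 42%/92%/99.9% of samples.

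The direction matters. With 15% large responders and mean change set to zero, false claims of worsening at n = 12 are about 13% and false claims of improvement about 0.5%, against a nominal 2.5% each. At n = 50 the figures are about 4 to 6% and 1%.

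**3. Dependence on stream size.** With outcomes uniform on 20 to 95, the switch fires in about 12% of samples at n = 12 and about 76% at n = 50. If the check is run within streams, the same outcome could be tested differently only because streams differ in size.

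**The case against.** **The outcomes may mean changes.** The objectives name most endpoints as changes, the t-test is placed on a difference, and the model description speaks of results "with change indexed relative to each individual's own personal baseline". This is a fair ambiguity. But the statistical section speaks of improvement in outcomes and of outcomes at the last visit, so there the word denotes the measure and improvement or change denotes the difference. If changes were meant, the plan does not say so.

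**Goal attainment is unaffected.** Its baseline is set at −1 for everyone, so follow-up score and change have the same shape. This stands as an exception.

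**The magnitudes are assumed.** So they are. The plan gives no SDs, no stream sizes and no normality check, and it does not state that the check is run per stream. The simulations show what the rule can do, not what it will do.

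**The study is an exploratory pilot and also plans mixed models.** True. This limits how much rests on the pre/post test.

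Stronger readings that a reader might infer are not supported:
- *The rule also governs the mixed model.* Only the paired t-test and Pearson's correlation are replaced. All that can be said of the model is that no residual check is stated.
- *The correlation switch is the same error.* For Pearson against Spearman, the variables' own distributions are relevant.
- *The trigger alone destroys power.* With a rank fallback it costs 1 to 2 points.
- *Improvement will be falsely declared more often.* With a few large responders, the excess is in false worsening.

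**Conclusion.** The point holds in a limited form. On the plain reading, the rule judges the paired t-test by the wrong quantity and can replace a valid test with one that needs an undefined dichotomy. Under the assumed bimodal scores with normal changes, power at a half-SD change falls by 22, 57 and 63 points at n = 12, 25 and 50. Nearly all of that needs both the trigger and McNemar.

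The opposite error, keeping a t-test on skewed changes, matters mainly in small streams and is slight near n = 50. A reader might conclude that valid tests are always dropped and invalid ones always kept. The documents do not support that: both outcomes are possible and depend on data not yet seen.

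The change should be made because the rule as stated can give a worse result than a fixed method, and correcting it is nearly free.

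**What to change.** Delete the data-driven switch for the paired test. State one method per outcome in advance, used in every stream and at every visit:

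- **Ordinal grades** (Ashworth, Keenan, House): Wilcoxon signed-rank test on the paired changes.
- **Degrees, DASH, pain, block count and grip in kg**: mean paired change with a t, bootstrap or permutation interval.
- **Goal attainment**: name a method too. With a constant baseline, this amounts to analysing the follow-up score against −1.
- **McNemar's test**: keep it only for a binary responder endpoint whose cut-off is defined in advance.
- **Any remaining assumption check**: within-patient differences for the paired test, residuals for the mixed model.

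Merely moving the normality check to the differences is not enough, because the test chosen would still depend on stream size.

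The cost is one or two sentences of analysis wording, with no new data and no extra patients.
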